7. OUTCOME ASSESSMENTS

7.1. Bleeding

Bleeding for the purpose of endpoints will be classified according to the ISTH definitions (see Section 17.1.1 and Section 9.1.1). Bleeding events will also be classified according to BARC (Section 17.1.3), TIMI (Section 17.1.2), and GUSTO (Section 17.1.4) classifications.

7.2. Primary Efficacy Parameters

NACE, i.e., the composite of all-cause death, MI, ischemic stroke, SEE, valve thrombosis, and major bleeding (ISTH definition)

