7.4. Secondary Endpoints (All Exploratory)

7.4.1. Secondary Efficacy Endpoints

- NACE defined as the composite of all-cause death, MI, ischemic stroke, SEE, valve thrombosis, and major bleeding (TIMI definition);
- NACE defined as the composite of all-cause death, MI, ischemic stroke, SEE, valve thrombosis, and major bleeding (BARC 3 or 5 definition);
- NACE defined as the composite of all-cause death, MI, ischemic stroke, SEE, valve thrombosis, and major and moderate bleeding (GUSTO definition);
- Major Adverse Cardiac Events (MACE), defined as the composite of all-cause death (excluding adjudicated non-cardiac death), MI, or repeat coronary revascularization of the target lesion;
- Major Adverse Cardiac and Cerebrovascular Events (MACCE), defined as the composite of all-cause death (excluding adjudicated non-cardiac death), MI, stroke (ischemic, hemorrhagic, or undetermined), or repeat coronary revascularization of the target lesion;
- Cardiovascular mortality
- Stroke (ischemic, hemorrhagic, or undetermined);
- Stroke (ischemic);
- Stroke (hemorrhagic);
- Stroke (undetermined)
- Fatal stroke (ischemic, hemorrhagic, or undetermined);
- Non-fatal stroke (ischemic, hemorrhagic, or undetermined);
- SEE;
- Myocardial Infarction;
- Valve thrombosis;

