11.4.2. Analyses of the secondary exploratory endpoints

The main analyses for all secondary efficacy and safety endpoints will be based on first occurrence of an (adjudicated) endpoint during the 'overall study period' for all subjects belonging to the ITT analysis set and applying the aforementioned statistical method.

There will be no formal statistical testing for secondary exploratory endpoints. HRs, CI and p-values are provided but should be interpreted in a purely descriptive exploratory manner.

To evaluate the robustness of the main analyses, the analysis will be repeated using the mITT and PP analysis set. In addition, the statistical results based on the following analysis periods: 'initial dose to final dose + 30 days' and 'overall study period + 30 days' will be presented but should be interpreted as supportive. Results for other combinations of analysis sets and analysis periods may be presented if considered necessary.

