17.1. Bleeding Criteria

17.1.1. ISTH Bleeding Criteria

Table 17.2: ISTH Bleeding Criteria²⁷

ISTH Bleeding Criteria

Major bleeding
 
 • Clinically overt bleeding that is associated with: 
 ○ A fall in hemoglobin of 2 g/dL (1.24 mmol/L) or more, or ○ A transfusion of 2 or more units of whole blood or packed red blood cells, or ○ Symptomatic bleeding in a critical site or organ such as: intracranial, intraspinal, intraocular, retroperitoneal, pericardial, intra-articular, intramuscular with compartment syndrome, or ○ A fatal outcome

Clinically relevant non-major (CRNM) bleeding
 
 • Any sign or symptom of hemorrhage (e.g., more bleeding than would be expected for a clinical circumstance, including bleeding found by imaging alone) that does not fit the criteria for the ISTH definition of major bleeding but does meet at least one of the following criteria: 
 ○ requiring medical intervention by a healthcare professional ○ leading to hospitalization or increased level of care ○ prompting a face to face (i.e., not just a telephone or electronic communication) evaluation.

Minor
 
 • Bleeding episodes not requiring any medical attention and therefore not meeting the criteria for major or clinically relevant non-major bleeding.

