17.3. Cerebrovascular event

Stroke is defined as an abrupt onset, over minutes to hours, of a focal neurological deficit that is generally in the distribution of a single brain artery (including the retinal artery) and that is not due to an identifiable non-vascular cause (i.e., brain tumor or trauma). The deficit must either be associated with symptoms lasting more than 24 hours or result in death within 24 hours of symptom onset.

TIA is defined as an abrupt onset, over minutes to hours, of a focal non-fatal, neurological deficit in the distribution of a single brain artery (including the retinal artery) that lasts less than 24 hours and that does not satisfy the definition of stroke above.

17.3.1. Stroke is classified according to the VARC-2 definitions.

Diagnostic criteria

- Acute episode of a focal or global neurological deficit with at least one of the following: change in the level of consciousness, hemiplegia, hemiparesis, numbness, or sensory loss affecting one side of the body, dysphasia or aphasia, hemianopia, amaurosis fugax, or other neurological signs or symptoms consistent with stroke

- Stroke – duration of a focal or global neurological deficit >24 h; OR <24 h if available neuroimaging documents, a new haemorrhage or infarct; OR the neurological deficit results in death
- No other readily identifiable non-stroke cause for the clinical presentation (e.g. brain tumor, trauma, infection, hypoglycemia, peripheral lesion, pharmacological influences), to be determined by or in conjunction with the designated neurologist*
- Confirmation of the diagnosis by at least one of the following: neurologist or neurosurgical specialist; neuroimaging procedure (CT scan or brain MRI), but stroke may be diagnosed on clinical grounds alone

Stroke classification

- Ischemic: an acute episode of focal cerebral, spinal, or retinal dysfunction caused by infarction of the central nervous system tissue
- Hemorrhagic: an acute episode of focal or global cerebral or spinal dysfunction caused by intraparenchymal, intraventricular, or subarachnoid hemorrhage
- A stroke may be classified as undetermined if there is insufficient information to allow categorization as ischemic or hemorrhagic

Stroke definitions**

- Disabling stroke: an modified Rankin Scale (mRS) score of 2 or more at 90 days and an increase in at least one mRS category from an individual's pre-stroke baseline

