17.5. Systemic thromboembolism

Systemic thromboembolism [non-central nervous system] is defined as abrupt vascular insufficiency of an extremity or organ associated with clinical or radiological evidence of arterial occlusion in the absence of other likely mechanisms, (e.g., trauma, atherosclerosis, instrumentation). In the presence of atherosclerotic peripheral vascular disease, diagnosis of embolism to the lower extremities should be made with caution and requires angiographic demonstration of abrupt arterial occlusion.

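### The primary NACE omits non-fatal strokes of undetermined type, although under the protocol's own definitions each must be one of two types that NACE counts

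*Combined protocol and SAP*

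**What the plan says.** The protocol gives the same primary composite in the synopsis and in Sections 2.1.1, 7.2 and 11.4.1: "NACE, i.e., the composite of all-cause death, MI, ischemic stroke, SEE, valve thrombosis, and major bleeding (ISTH definition"). Ischemic stroke is the only stroke type listed.

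Section 17.3.1 classifies strokes as ischemic, hemorrhagic or undetermined. Hemorrhagic stroke is "an acute episode of focal or global cerebral or spinal dysfunction caused by intraparenchymal, intraventricular, or subarachnoid hemorrhage". On the third class it says: "A stroke may be classified as undetermined if there is insufficient information to allow categorization as ischemic or hemorrhagic". The same section allows a stroke to be diagnosed clinically, without imaging.

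Table 17.2 (Section 17.1.1) lists among the ISTH major bleeding criteria: "Symptomatic bleeding in a critical site or organ such as: intracranial, intraspinal". Section 17.5 keeps systemic embolism outside the brain and spinal cord: "Systemic thromboembolism [non-central nervous system] is defined as abrupt vascular insufficiency of an extremity or organ".

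Among the secondary endpoints in Section 7.4.1, MACCE includes "MI, stroke (ischemic, hemorrhagic, or undetermined), or repeat coronary revascularization of the target lesion", and "Stroke (undetermined") is an endpoint of its own. Section 11.4.2 makes these exploratory: "There will be no formal statistical testing for secondary exploratory endpoints".

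**The concern.** A sponsor may leave a type of event out of a composite. Here both possible types are in the composite, and the stroke drops out only because its type could not be established. Whether it counts therefore depends on how much diagnostic information reached the adjudicators, not on what happened to the subject.

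This deserves attention because the trial is open-label (Section 5.1.3). The CEC adjudicates blind, but sites know the assigned drug when they decide how far to investigate a suspected stroke. After discontinuation, Section 6.7 allows events to be learned from relatives, treating physicians or public records, where the type may be hard to establish. If the share of untyped strokes differed between arms, the primary hazard ratio would carry some of that difference. The documents contain no evidence that it would; it is a possible dependence that one phrase can remove.

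**Working it through.** **1. Routes into NACE for a stroke, by type**

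| Stroke type (17.3.1) | Route into primary NACE |
|---|---|
| Ischemic | Named component (7.2) |
| Hemorrhagic | ISTH major bleeding: symptomatic intracranial or intraspinal (Table 17.2) |
| Undetermined, fatal | All-cause death (7.2) |
| Undetermined, non-fatal | None |

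For the last row, each component was checked. It is not adjudicated as ischemic stroke. It cannot be systemic embolism, which is non-CNS by Section 17.5. It is not ISTH major bleeding without a bleed. MI and valve thrombosis do not apply. The subject remains event-free for NACE until another qualifying event or censoring.

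**2. Does the analysis plan repair this?** Section 11.4.1 varies the analysis set (mITT, PP) and the analysis period, not the endpoint definition. Section 11.2 imputes nothing. No sensitivity analysis adds undetermined strokes to NACE.

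**3. Does the argument carry over to the other NACE versions?** It does only where every hemorrhagic stroke in the sense of Section 17.3.1 (intraparenchymal, intraventricular or subarachnoid, cerebral or spinal) meets the bleeding criterion.

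- BARC 3 or 5: type 3c covers intracranial and expressly intraspinal hemorrhage (17.1.3). The argument holds.
- TIMI: major bleeding names intracranial hemorrhage but not spinal (17.1.2). It does not hold fully.
- GUSTO: severe bleeding names only intracerebral hemorrhage, apart from hemodynamic compromise (17.1.4). It does not hold for subarachnoid or spinal hemorrhage.

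**4. Number of events.** Section 6.5 gives about 2,500 subject-years. The other two inputs are assumptions: stroke 2-3% per year, and 3-10% of strokes undetermined.

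- Strokes: 2,500 × 0.02 = 50, to 2,500 × 0.03 = 75.
- Undetermined: 50 × 0.03 = 1.5, to 75 × 0.10 = 7.5.
- Relative to the 320 planned NACE: 1.5/320 = 0.5%, to 7.5/320 = 2.3%.

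This is an upper range. It includes fatal strokes, which count already. It also includes subjects with another NACE event: under first-event counting (Section 7.4.3) an earlier event means nothing is lost, and a later one means only that the event is dated late.

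**5. Effect on the hazard ratio, extreme case.** Take 160 events per arm and equal follow-up, and put 7 uncounted strokes all in one arm. The ratio of event counts moves from 1.00 to 167/160 = 1.04, against a margin of 1.38.

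**6. Effect on power if the events were simply added.** Schoenfeld power for noninferiority at 1:1 allocation is Φ(½√d × ln(1.38/HR) − 1.96).

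| Events d | HR 0.95 | HR 1.00 |
|---|---|---|
| 320 | 91.6% | 82.1% |
| 325 | 92.0% | 82.7% |
| 336 (5% more) | 92.8% | 83.9% |

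The plan's own 320 is not reproduced from its stated inputs: margin 1.38, HR 0.95, two-sided 0.05 and 80% power give 226 events by this formula. That is a separate matter. Here 320 serves only as the starting count.

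**The case against.** The strongest case against has four parts.

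*The omission may be deliberate.* The protocol lists undetermined stroke wherever it is wanted and leaves it out of NACE in every statement. MACCE has no bleeding component, so it has to name every stroke type, and its wording is weak evidence of an oversight. Requiring a positively typed event could be a choice for specificity, since an untyped stroke may also be a less certain diagnosis. This has some force, but no section gives that reason, and it does not explain excluding an event when both its possible types are in scope.

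*The design replaces lost events.* A reader might infer that the omission costs information or power. Section 11.9 requires at least 320 NACE, and Section 6.5 continues treatment until 320 are adjudicated. A few uncounted strokes mainly shift the date at which 320 is reached. This stands.

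*The causes are not documented.* A reader might also infer that these strokes are untyped because imaging was missing, or that they fall mainly on the frailest subjects. Section 17.3.1 speaks only of too little information, and nothing links it to frailty or to treatment arm. This stands, so differential work-up remains a possibility only.

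*It may be handled elsewhere.* The CEC Charter (Section 15.10) is not among the documents and may contain a rule. Undetermined stroke is also reported separately, so its frequency will be visible. Both are fair, but a rule that decides what the primary endpoint counts belongs in the protocol.

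**Conclusion.** The point holds for the ISTH-based primary NACE and, by the same reasoning, for the BARC 3 or 5 version. By the protocol's definitions a non-fatal undetermined stroke must be one of two NACE components, yet it is not counted, and no rule or planned analysis in the text corrects this.

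The benefit of correcting it is right classification and less dependence on diagnostic work-up, not added information. The size is very small: at most about 1 to 7 events under assumed rates that the documents do not supply, and fewer once fatal strokes and subjects with another NACE event are removed. It would not support a claim that the primary result is biased or underpowered.

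A reader might want to extend the change to all versions of NACE. The documents do not support that for TIMI or GUSTO, whose bleeding definitions do not name every kind of hemorrhagic stroke in Section 17.3.1.

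**What to change.** In the ISTH-based primary NACE, replace *ischemic stroke* with *stroke (ischemic or undetermined)*, and let hemorrhagic stroke continue to enter through major bleeding. Make the change wherever the composite is stated (synopsis and Sections 2.1.1, 7.2 and 11.4.1), and align the CEC Charter if it has no such rule. The BARC 3 or 5 version can be worded the same way. Leave the TIMI and GUSTO versions alone on this argument.

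If the sponsor prefers the current wording, state that the exclusion is intended and why, and prespecify a sensitivity analysis of NACE plus undetermined stroke.

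The cost is wording. Strokes are already classified by type, so no new data, visits or adjudication categories are needed. The downside is a slight change to the named composite.

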7.3. Primary Safety Parameters

Major bleeding (ISTH definition)

7.4. Secondary Endpoints (All Exploratory)

7.4.1. Secondary Efficacy Endpoints

- NACE defined as the composite of all-cause death, MI, ischemic stroke, SEE, valve thrombosis, and major bleeding (TIMI definition);
- NACE defined as the composite of all-cause death, MI, ischemic stroke, SEE, valve thrombosis, and major bleeding (BARC 3 or 5 definition);
- NACE defined as the composite of all-cause death, MI, ischemic stroke, SEE, valve thrombosis, and major and moderate bleeding (GUSTO definition);
- Major Adverse Cardiac Events (MACE), defined as the composite of all-cause death (excluding adjudicated non-cardiac death), MI, or repeat coronary revascularization of the target lesion;
- Major Adverse Cardiac and Cerebrovascular Events (MACCE), defined as the composite of all-cause death (excluding adjudicated non-cardiac death), MI, stroke (ischemic, hemorrhagic, or undetermined), or repeat coronary revascularization of the target lesion;
- Cardiovascular mortality
- Stroke (ischemic, hemorrhagic, or undetermined);
- Stroke (ischemic);
- Stroke (hemorrhagic);
- Stroke (undetermined)
- Fatal stroke (ischemic, hemorrhagic, or undetermined);
- Non-fatal stroke (ischemic, hemorrhagic, or undetermined);
- SEE;
- Myocardial Infarction;
- Valve thrombosis;

7.4.2. Secondary Safety Endpoints

- Bleeding defined as TIMI major or minor, BARC 3 or 5, and GUSTO moderate or severe;
- Bleeding defined as ISTH major and CRNM; TIMI major/minor bleeds or requiring medical attention; BARC 2, 3 or 5; and GUSTO moderate or severe;
- Bleeding defined as ISTH CRNM, TIMI minor or requiring medical attention, BARC 2, and GUSTO moderate;
- All bleeding that are not ISTH major, CRNM, TIMI minimal, BARC 1 non-actionable, and GUSTO mild;
- Any bleeding;
- Intracranial hemorrhage;
- Life-threatening bleeding;
- Fatal bleeding (fulfilling the ISTH major bleeding definition);
- Non-fatal major bleeding (ISTH definition);
- All-cause mortality;
- Cardiovascular mortality;
- Safety parameters such as (serious) adverse events, laboratory parameters, ECG and vital signs

7.4.3. Other Endpoints

- Number of hospital admissions, defined as ≥ 24 h stay in the hospital, due to cardiovascular causes (post TAVI and non-TAVI procedure related), including but not limited to overall, for bleeding, SEE, venous thrombosis, shock, arrhythmia, cardiac rupture, stroke, aneurysms, stent occlusions, etc.
 - Note: Hospital admissions due to cardiovascular causes include, but are not limited to the Emergency Department, ICU, and cardiovascular ward.
- Treatment satisfaction as assessed by the PACT-Q
- Health related quality of life as assessed by the EQ-5D-5L Questionnaire
- Optional: Sub-studies not interfering with the main study may be added including such as the assessment of biomarkers of hemostasis/coagulation and of cardiovascular risk such as but not limited to WBCT, TEG, and MEA, Hs-TnT, GDF-15, and cystatin-C.

All clinical endpoints will be analyzed as time to first occurrence of any of its components.

All relevant NACE components will be adjudicated by the CEC in a blinded manner. For all clinical endpoints blindly adjudicated by the CEC, the CEC's interpretation prevails and will be used in the statistical analysis.

8. PHARMACOKINETIC/PHARMACODYNAMIC ASSESSMENTS

Not applicable

8.1. Immunogenicity

Not applicable

8.2. Pharmacogenomic Analyses

Not applicable

9. SAFETY EVALUATION AND REPORTING

Safety assessments that are components of the study endpoint assessments (e.g., bleeding endpoints) are detailed in Section 7.3 and Section 7.4.2 and must be collected in the AE/Outcome eCRF page(s).

9.1. Adverse Event Collection and Reporting

All clinical AEs (see Section 9.3.1 for definitions) occurring after the subject signs the Informed Consent Form and up to 30 days after the last dose of study medication (i.e., the follow-up period), whether observed by the Investigator or reported by the subject, will be recorded on the Adverse Event eCRF page.

Subjects who permanently discontinue study medication but continue in the study will be followed up every 6 months for collection of vital status (not vital signs) including collection of SAE and/or endpoint event reporting until the end of study (see Section 6.7).

Medical conditions (including laboratory values/vital signs that are out of range) that were diagnosed or known to exist prior to Informed Consent will be recorded as part of medical history.

All serious adverse events (SAEs), are to be reported according to the procedures in Section 9.6.

- All laboratory results, vital signs, ECG, and any other imaging results or findings should be appraised by the Investigator to determine their clinical significance. Isolated abnormal laboratory results, vital sign findings, or ECG findings (i.e., not part of a reported diagnosis) should be reported as AEs if they are symptomatic, lead to study drug discontinuation, dose reduction, require corrective treatment, or constitute an AE in the Investigator's clinical judgment.
- At each visit, the Investigator or qualified designee will determine whether any AEs have occurred by evaluating the subject. Adverse events may be directly observed, reported spontaneously by the subject, or by questioning the subject at each study visit. Subjects should be questioned in a general way, without asking about the occurrence of any specific symptoms. The Investigator must assess all AEs to determine seriousness, severity, and causality, in accordance with the definitions in Section 9.3. The Investigator's assessment must be clearly documented in the site's source documentation with the Investigator's signature.

Always report the diagnosis as the AE or SAE term. When a diagnosis is unavailable, report the primary sign or symptom as the AE or SAE term with additional details included in the narrative until the diagnosis becomes available. If the signs and symptoms are distinct and do not suggest a common diagnosis, report them as individual entries of AE or SAE.

For events that are defined as serious due to hospitalization, the reason for hospitalization must be reported as the serious adverse event (diagnosis or symptom requiring

hospitalization). A procedure is not an AE or SAE, but the reason for the procedure may be an AE or SAE.

Pre-planned (prior to signing the ICF) procedure or treatment requiring hospitalization for pre-existing conditions which do not worsen in severity should not be reported as SAEs (see Section 9.3.4 for definitions).

For deaths, the underlying or immediate cause of death should always be reported as an SAE.

Any serious, untoward event that may occur subsequent to the reporting period that the Investigator assesses as related to study drug should also be reported and managed as an SAE.

Investigator should follow subjects with adverse events until the event has resolved or the condition has stabilized. In case of unresolved adverse events including significant abnormal laboratory values at the end of study assessment, these events will be followed up until resolution or until they become clinically not relevant.

In the following differentiation between medical history and AEs, the term “condition” may include abnormal physical examination findings, symptoms, diseases, laboratory, ECG, or any other imaging findings:

Conditions that started before signing of informed consent and for which no symptoms or treatment are present until signing of informed consent are recorded as medical history (e.g., seasonal allergy without acute complaints).

Conditions that started before signing of informed consent and for which symptoms or treatment are present after signing of informed consent, at unchanged intensity, are recorded as medical history (e.g., allergic pollinosis).

Conditions that started or deteriorated after the first dose of drug will be documented as adverse events; these include intercurrent illnesses.

